6.3.1.2. Analysis

Frequency and types of interventions during the 12-week treatment period will be summarized as count data using descriptive statistics. In addition, similar Bayesian analysis specified for primary endpoint will be performed for those variables separately using Poisson regression. The suggested SAS code for the analyses is as follows:

```
proc mcmc data = x nbi = 1000 nmc = 100000 thin = 20 seed = 159 outpost = post2
  monitor = (beta0-beta3 sigma2 beta1_gt0 lambda lambda0 pooled) statistics=(summary
  intervals);
  parms beta0-beta3 0;
  parms sigma2 1;
  prior beta0-beta3 ~ normal(mean = 0, var = 1000);
  prior sigma2 ~ igamma(shape = 0.001, scale = 0.001);
  random b0 ~ normal(mean = 0, var = sigma2) subject = CENTER;
  eta = beta0 + b0 + beta1*trt + beta2*logt + beta3*y0;
  lambda = exp(eta);
  lambda0 = exp(beta0 + b0 + beta2*logt + beta3*y0);
  model hosp ~ poisson(lambda);
  array lmda[<# of sites>];
  lmda[CENTER] = exp(b0 + beta1 + beta2*logt + beta3*y0);
  pooled = exp(beta1);
  beta1_gt0 = beta1 < 0;
run;
```

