2.4. Sample Size and Power Considerations

Sample size estimates are based upon the assumption that the absolute differences between the DS and CC group and the associated operational characteristics will be similar to the absolute differences and operational characteristics of the DS and CC groups noted in the sample size rationale for the study design.

The recommended sample size for the study is 150 evaluable patients per group (30 investigational centers with each investigational center enrolling at least 10 patients), 300 patients in total. Accounting for a dropout rate of 10%, this leads to a recommended total number of 330 enrolled patients.

With this sample size and assuming a true absolute difference in proportions (treatment effect as the estimated response rate for the CC group is 60% and for the DS group is 73%) between the groups of at least 13%, the probability that the posterior probability will be at least 95% is 0.77 (power) (analogous to 1-sided p-value < 0.05) ([Merchant et al 2016](#)). Assuming no treatment effect (difference in proportions between the groups is 0%, ie, Type 1 error) then the probability is 0.05 that posterior probability will be at least 95% is 0.05.

It should be noted that both power and Type 1 error are dependent on the absolute difference between the DS and the CC groups as illustrated in Figure 5 of the study protocol by the operational characteristics calculated for the study design.

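### The Poisson model for intervention counts (SAP 6.3.1.2) has no between-patient variance term, so its credible intervals will be too narrow if recurring actions vary between patients beyond Poisson

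*SAP*

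**What the plan says.** SAP 6.3.1.2 first plans descriptive summaries of the frequency and type of intervention over the 12 weeks. It then adds that a "similar Bayesian analysis specified for primary endpoint will be performed for those variables separately using Poisson regression". The choice of Poisson is therefore in the prose, although the program that follows is introduced more loosely: "The suggested SAS code for the analyses is as follows".

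In that program:

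- The likelihood is "model hosp ~ poisson(lambda").
- The linear predictor has an intercept, treatment, `logt`, `y0` and a center effect. The section does not define `logt` or `y0`. I read them as log follow-up time and a baseline covariate.
- The only random term is "random b0 ~ normal(mean = 0, var = sigma2) subject = CENTER".
- The coefficient priors are vague: "prior beta0-beta3 ~ normal(mean = 0, var = 1000").
- The output includes interval summaries, the rate ratio exp(beta1), and a posterior probability coded as "beta1_gt0 = beta1 < 0". The mismatch between that variable's name and its definition is a separate matter.

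Neither document gives a dispersion parameter, a patient-level effect, a check for overdispersion or a fallback model for these counts. SAP section 7 groups secondary endpoint #1 with the primary endpoint as analysed by Bayesian methods. Protocol 9.5.4.3 plans descriptive analysis only for all secondary endpoints.

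**The concern.** A Poisson likelihood forces each patient's count variance to equal its mean once the terms in the linear predictor are fixed. Patients in the same center with the same arm, `logt` and `y0` are then assumed to share one rate.

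The structure is carried over from the primary analysis. That outcome is one yes/no per patient and cannot be overdispersed at patient level. A count can be.

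The study gives some reason to expect differences between patients. Under Protocol 3.1 and Appendix B, contacts other than Visit 2 happen only when the provider or patient sees a need, and no clinical decision is prescribed. A patient with several contacts can accumulate several discussions or adjustments, and another patient none.

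At stake is how the comparison of management actions between arms is read. This endpoint describes how clinicians use the Digital System in an open-label trial. An interval that is too narrow can make chance variation between arms look like a difference in management.

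**Working it through.** **Inputs from the documents.** "150 evaluable patients per group" (SAP 2.4); 30 centers and 1:1 allocation within center (SAP 2.2 and 2.4), hence 5 per arm per center in a balanced layout; model and priors from SAP 6.3.1.2.

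**Assumed inputs.** The mean count per patient, mu, and the between-patient dispersion, k. The documents state neither, so a range is shown.

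**The plan's own figure.** No power or precision is stated for this endpoint. The only design figure is the power of 0.77 for the primary endpoint. It reproduces: with 60% and 73% and 150 per arm, the null standard error is sqrt(2 × 0.665 × 0.335/150) = 0.0545 and the alternative one is sqrt((0.24 + 0.1971)/150) = 0.0540. Then Phi((0.13 − 1.645 × 0.0545)/0.0540) = 0.773. This confirms the design inputs but does not bear on the count model.

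**Closed form.** Let patient rates vary as a gamma distribution with dispersion k.

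1. Count variance = mu(1 + k mu), so the variance/mean ratio is D = 1 + k mu.
2. Standard error of the log rate ratio assumed by the Poisson model: sqrt(2/(150 mu)). Actual value: sqrt(2D/(150 mu)). The understatement factor is sqrt(D).
3. With vague priors, coverage of the nominal 95% interval is approximately 2 Phi(1.96/sqrt(D)) − 1.

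At mu = 1 the assumed standard error is sqrt(2/150) = 0.115. At D = 2 the actual one is sqrt(4/150) = 0.163.

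| Assumed situation | D | sqrt(D) | Coverage |
|---|---|---|---|
| No extra variation | 1 | 1.00 | 95.0% |
| mu = 0.1, k = 1 | 1.1 | 1.05 | 93.8% |
| mu = 0.25, k = 1 | 1.25 | 1.12 | 92.0% |
| mu = 1, k = 0.5 | 1.5 | 1.22 | 89.0% |
| mu = 1, k = 1 | 2 | 1.41 | 83.4% |
| mu = 1, k = 2 | 3 | 1.73 | 74.2% |
| At most once, probability 0.3 (D = 1 − 0.3) | 0.7 | 0.84 | 98.1% |
| At most once, probability 0.5 (D = 1 − 0.5) | 0.5 | 0.71 | 99.4% |

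**Does the center effect absorb it?** No. In 4000 simulated trials per setting, with 30 centers of 5 per arm and a center-adjusted Poisson estimate at mu = 1, coverage was 94.8%, 88.5%, 82.6% and 72.9% for k = 0, 0.5, 1 and 2.

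**Do the Bayesian fit and its priors change it?** No. The random center intercept and priors of SAP 6.3.1.2 were fitted by MCMC, without `logt` and `y0`, to 450 trials with mu = 1, k = 1 and center SD 0.3. Coverage was about 81% with mean interval width 0.45. A negative binomial likelihood in the same structure gave about 93% and 0.65.

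**Would summing by center and arm help?** No. The sum of m counts has mean m mu and variance m mu D, so the ratio is unchanged.

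**Cost of the remedy when it is not needed.** With no extra variation, a dispersion correction widened intervals by about 2% in simulation. In 100 MCMC fits the negative binomial interval averaged 0.463 against 0.442, about 5% wider.

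**The case against.** The strongest objection is that the extra variation is assumed. That stands. A reader might infer that these counts do cluster within patients, but the documents report no distribution for them, and the contact rules only make clustering plausible. The direction is not settled either. Some listed actions, such as starting a biologic, may happen at most once per patient. For those the Poisson interval is conservative, and a negative binomial cannot represent them. For rare actions the loss of coverage is only one to three points.

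A second objection is that nothing is decided on this model, and that also stands. A reader might carry over the primary endpoint's 0.95 posterior criterion and conclude that the false-positive rate rises above 5%. The 0.95 criterion is stated only for the primary endpoint (SAP 6.2.2). SAP section 7 disclaims hypothesis testing, and no threshold is given for endpoint #1.

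Third, the descriptive summaries come first and the code is only suggested. If means and standard deviations are reported for the counts, a reader could spot overdispersion. That is partial mitigation. It does not correct the intervals, and the Poisson choice is in the prose as well as the code.

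What the objections leave intact is that the SAP will report credible intervals and a posterior probability from this model, and these should be calibrated.

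**Conclusion.** The point holds conditionally and is minor. If recurring actions vary between patients beyond Poisson after `logt`, `y0` and center, the intervals in SAP 6.3.1.2 are too narrow by a factor of sqrt(D), and the posterior probability is too extreme. Under the assumed values, at a mean of 1 and D from 1.5 to 3, the factor is 1.22 to 1.73 and coverage falls to between 89% and 74%. The effect is slight for rare actions, absent without extra variation, and reversed for actions possible only once.

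The consequence is confined to a supplementary analysis of a secondary endpoint. The primary analysis and the sample size are untouched.

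**What to change.** In SAP 6.3.1.2, separate the intervention variables into those that can recur and those that can occur at most once per patient.

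- **Counts that can recur:** replace the Poisson likelihood by a negative binomial, or add a normal patient-level random effect to the linear predictor (one record per patient). Keep the center effect. State a weakly informative prior for the new parameter. For example, the negative binomial check above used a normal prior with mean 0 and SD 2 on log k.
- **Actions possible at most once:** analyse as binary, with the logistic structure already written for the primary endpoint.

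The cost is a short SAP edit before database lock, one extra parameter with its prior, and a few changed lines of code. If there is no extra variation, intervals widen slightly (about 2% to 5% in the checks above).

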6.3.2. Secondary Endpoint #2 – Evaluation of Short-Acting Beta₂ Agonists Usage

6.3.2.1. Definition

Secondary endpoint #2 is the change from week 1 in the mean weekly SABA usage and the change from week 1 in the number of SABA-free days over the 12-week treatment period for the DS group. SABA usage and SABA-free days. Weekly average SABA use will be defined as ((number of inhalations in a week)*90 ug/7) and change from week 1 in weekly average SABA use will be defined as (week i – week 1). Weekly SABA-free days will be defined as number of days a patient does not use the rescue medication in a week. If no inhalations done for any week, the amount of the SABA use will be 0 and SABA-free days for week will 7.

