5.1.1. Test Investigational Medicinal Product

[figure not shown]
Albuterol eMDPI (marketed in the US as PROAIR DIGIHALER) is an inhalation-driven eMDPI containing a blend of albuterol sulfate and alpha-lactose monohydrate. The inhaler contains 200 actuations, each delivering 90 mcg of albuterol base ex-mouthpiece; the inhaler is equipped with a dose counter that shows only even numbers and counts down to “0.”

The plastic inhaler comprises a reservoir containing inhalation powder, a metering system, a mouthpiece with dust cover, and an eModule sitting on top of the drug-delivery compartment. Teva has developed the eModule as part of a system to assist a patient with asthma to appropriately use the eMDPI inhaler. The system is described in more practical terms as an inhaler with an integrated data logger capable of storing and transmitting timestamped data to support the data logging functionality.

The on-board electronics and power source are fully integrated into the eMDPI and are designed to operate for the life of the inhaler without intervention, ie, the battery does not require replacement or recharging.

The addition of the required electronics has no impact on the pharmaceutical performance of the inhaler or on the required user steps to take a dose. A schematic of the inhaler with the additional eModule is shown in [Figure 3](#).

Figure 3: Current Inhaler (Left) Versus Inhaler with Additional Electronics Module (Right)

Additional details may be found in [Table 4](#) and in the IB.

The information from the eModule may be transmitted wirelessly (Bluetooth Low Energy) to an App. From the App, data may be transmitted to the DHP, which consists of a Cloud solution, and then to a dashboard. This allows the patient and/or the caregiver to track when and how well the inhaler was used.

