9.5.2. Secondary Endpoints

Secondary endpoint #1 is the frequency and types of interventions done to improve asthma control including:

- number of discussions between patient and iHCP regarding inhaler technique or adherence
- number of adjustments of therapy including:
 - increased or decreased doses of inhaled medication
 - change to different inhaled medication
 - additional inhaled medication
 - addition of a systemic corticosteroid medication for asthma or another controller, including a LAMA or biologics
- frequency of intervention to manage comorbid conditions associated with poor asthma control (GERD, sinusitis, etc.)

Secondary endpoint #2 is the change from baseline in the mean weekly SABA usage and the change from baseline in the number of SABA-free days over the 12-week treatment period for the DS group.

Secondary endpoint #3 is the assessment of the DS (eMDPI, App and dashboard) acceptability and usability, utilizing the SUS, completed by the patients in the DS group, 18 years of age or older, and investigational center personnel at the end of the study.

Secondary endpoint #4 is the assessment of patients' beliefs and perceptions about their disease and treatment, utilizing the BMQ and the BIPQ for both the DS and CC groups, patients 18 years of age or older, describing their behavioral profile at baseline and at the end of the study.

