1. STUDY OBJECTIVES AND ENDPOINTS

1.1. Primary and Secondary Study Objectives and Endpoints

The primary and secondary study objectives and endpoints are:

Objectives	Endpoints
The primary objective of this study is to demonstrate the effectiveness of the Digital System (DS) compared to a concurrent control (CC) group.	The primary endpoint is the proportion of patients for the DS and CC groups achieving meaningful improvement, which is defined as an Asthma Control Test (ACT) score greater than or equal to 20 at the end of the 12-week treatment period or an increase of at least 3 units on the ACT score from baseline at the end of the 12-week treatment period.
The secondary objective (#1) is to describe the asthma management actions by investigational center healthcare providers (iHCPs) for all patients in both groups.	
This secondary endpoint will describe the frequency and types of interventions done to improve asthma control including:
 
 • number of discussions between patient and healthcare provider (HCP) regarding inhaler technique or adherence • number of adjustments of therapy including: 
 ◦ increased or decreased doses of inhaled medication ◦ change to different inhaled medication ◦ additional inhaled medication ◦ addition of a systemic corticosteroid medication for asthma or another controller, including a long-acting muscarinic antagonist (LAMA) or biologics • frequency of intervention to manage comorbid conditions associated with poor asthma control (gastroesophageal reflux disease [GERD], sinusitis, etc.)
The secondary objective (#2) is to evaluate short-acting beta ₂ agonist (SABA) usage and the number of SABA-free days in the DS group.	This secondary endpoint is the change from baseline in the mean weekly SABA usage and the change from baseline in the number of SABA-free days over the 12-week treatment period for the DS group.
The secondary objective (#3) is to assess the usability and acceptability of the DS by patients in the DS group and the investigational center personnel.	This secondary endpoint is the assessment of the DS (eMDPI, App and dashboard) acceptability and usability, utilizing the System Usability Scale (SUS), completed by the patients in the DS group, 18 years of age or older, and the investigational center personnel at the end of the study.

Objectives	Endpoints

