4.4. Study Days and Visits

Study days are numbered relative to the treatment start date (ie, ..., -2, -1, 1, 2, ...; with day 1 being the treatment start date and day -1 being the day before the treatment start date).

Weeks are defined in 7-day intervals (days 1 to 7, 8 to 14, ..., 78 to 84). Day 1 is defined as the treatment start date (i.e., date of randomization/Visit 1 visit date).

By-visit (or by-week) summaries will include baseline, and the end of treatment and ET visits.
The ET visit will be summarized as a separate visit.

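### Weekly SABA use in SAP 6.3.2.1 is divided by a fixed 7, so a week only partly on study reads as reduced rescue use; the variable also lacks a unit, which is µg per day

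*SAP*

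**What the plan says.** The protocol and the SAP objectives name the endpoint alike. Protocol 9.5.2: "Secondary endpoint #2 is the change from baseline in the mean weekly SABA usage". SAP 1.1: "This secondary endpoint is the change from baseline in the mean weekly SABA usage". Both restrict it to the DS group over the 12-week treatment period.

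SAP 6.3.2.1 makes it operational, with week 1 as the reference: "Secondary endpoint #2 is the change from week 1 in the mean weekly SABA usage". The variable is then given by formula: "Weekly average SABA use will be defined as ((number of inhalations in a week)*90 ug/7". The change score uses the same scale: "change from week 1 in weekly average SABA use will be defined as (week i – week 1". SABA-free days are a count per week of days without rescue use. A further rule covers empty weeks: "If no inhalations done for any week, the amount of the SABA use will be 0", with SABA-free days set to 7.

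The week itself is fixed in SAP 4.4: "Weeks are defined in 7-day intervals (days 1 to 7, 8 to 14, ..., 78 to 84". Under SAP 4.1, treatment ends at the end-of-treatment or ET visit, or at last contact if that date is missing, so it can end inside a week. SAP 3.2 keeps early terminators in the mITT set after one dose and one postbaseline assessment. SAP 4.3 gives rules for missing data or discontinuation for the primary endpoint, SUS, BMQ and BIPQ, but none for SABA use. SAP 6.3.2.2 summarises the variables descriptively.

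**The concern.** Two separate things need attention.

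The first is the unit. Inhalations in a week, times µg per inhalation, divided by 7, is µg per day. Neither document says so, and the endpoint is called mean weekly usage. SABA-free days in the same paragraph are a count per week, so the two halves of one endpoint use different time bases under the word weekly. Someone reading 180 in a table could take it as a weekly total (2 inhalations a week) when it means 2 inhalations a day.

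The second is the fixed divisor. In a week with fewer than 7 days on study, dividing by 7 treats the missing days as days without use. That sits badly with Protocol 9.3, which plans to use observed data only unless the SAP specifies otherwise. The error has one direction, towards lower use, which is the favourable one. Because the endpoint is DS-only, no control group shares it.

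**Working it through.** The documents give no expected value for this endpoint, so there is no stated figure to reproduce. The formula can be evaluated directly.

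**Inputs.** Dose per inhalation: 90 µg, from Protocol 5.1.1 ("each delivering 90 mcg of albuterol base ex-mouthpiece"). Divisor: 7, from SAP 6.3.2.1. Assumed for illustration: 2 inhalations a day.

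**Complete week.** 14 inhalations. SAP value = 14 × 90 / 7 = 180, the daily dose in µg. Weekly total = 14 × 90 = 1260 µg. The ratio is 1/7 whatever the count.

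**Does the factor 7 matter for change?** Going from 28 to 14 inhalations a week: (14 − 28) × 90 / 7 = −180 on the SAP scale and (14 − 28) × 90 = −1260 as a weekly total. Both are −50%. Only the unit differs.

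**Week with d days on study, use unchanged at 2 a day.** SAP value = 2d × 90 / 7 = 180 × d/7. Dividing by days on study gives 2d × 90 / d = 180.

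| Days on study | SAP value | Divided by days on study |
|---|---|---|
| 1 | 25.7 | 180 |
| 2 | 51.4 | 180 |
| 3 | 77.1 | 180 |
| 4 | 102.9 | 180 |
| 5 | 128.6 | 180 |
| 6 | 154.3 | 180 |
| 7 | 180.0 | 180 |

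With 3 days, the change from a complete week 1 is 77.1 − 180 = −102.9 µg/day although use did not change. A weekly total does not escape this: 6 × 90 = 540 µg against 1260.

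**SABA-free days in the same 3-day week.** If every day without a record counts as free, the patient who used the inhaler on all 3 days scores 7 − 3 = 4 instead of 0. If only days on study count, the maximum is 3 rather than 7. The SAP does not say which applies.

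**Who is affected.** Protocol Table 3 places Visit 2 at Day 84 with a window of up to 7 days later and none earlier, and the last analysis week ends on day 84. A completer seen on schedule therefore has 12 full weeks. Partial weeks arise mainly from early termination, at most one per patient.

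**Expected effect on a weekly mean.** Assumptions: 330 / 2 = 165 DS patients; the planned 10% dropout, so 16.5 patients; leaving spread evenly over 12 weeks; about half the final week lost on average; leavers with the same use as others; partial weeks kept in the summary.

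- Partial weeks per weekly summary: 16.5 / 12 = 1.375.
- Share of patients: 1.375 / 165 = 0.83%. Among those still present at the start of week 12, it is 1.375 / (165 − 16.5 × 11/12) = 1.375 / 149.9 = 0.92%.
- Shift in the mean: 0.83% × 0.5 = 0.42%, up to 0.92% × 0.5 = 0.46%. At 180 µg/day that is about 0.8 µg/day.

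**The case against.** The formula is written out in full, and an average over a week is ordinarily the sum divided by 7. Read as the daily average within each week, the variable's name and its formula agree, and anyone with the SAP can see the scale. This stands. A reader might infer that the SAP has made an arithmetic error and that reported use is wrong by a factor of seven. The documents do not support that: no calculation is wrong, and no table shell shows how the values will be labelled. What remains is a missing unit and a loose fit with the endpoint's name.

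The endpoint is also descriptive and DS-only, and no test, decision rule or power figure uses it. That stands too and limits the importance of the whole point.

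On partial weeks, it can be said that the documents do not state that such weeks are kept. True, but they do not state that they are dropped either, and the formula as written yields a value for them. The defence that the mean barely moves is fair for the mean. It does not cover the individual change scores or the minimum, which SAP 4.1 lists among the statistics to be shown.

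**Conclusion.** The point holds as a minor one. The unit and label need aligning, with no effect on direction or percent change. The fixed divisor does give a wrong value, d/7 of true daily use, in a week partly on study. The shift in a weekly mean is about 0.4% to 0.5% under the assumptions above. It would be larger in µg if patients who leave use more rescue medication than those who stay, and larger as a share of the mean change if that change is small.

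Two stronger inferences should not be drawn. One is that final weeks in general look like reduced use; the Visit 2 window gives scheduled completers 12 full weeks. The other is that the zero rule scores every week after discontinuation as 0 µg and 7 SABA-free days. That would matter more: by week 12, 16.5 × 11/12 = 15.1 of 165 patients, or 9.2%, would carry false zeros. But the documents do not plan this. The endpoint is defined over the treatment period, SAP 4.1 ends treatment at the ET visit, and Protocol 9.3 favours observed data. The wording merely fails to rule it out.

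**What to change.** Amend SAP 6.3.2.1 before database lock:

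- Define mean daily SABA use in a week, in µg/day, as 90 × inhalations in the week divided by days on study in that week. If a weekly figure is to be reported, multiply by 7 and label it µg/week. Use the same name and unit in the endpoint wording and the tables.
- Define days on study from the treatment start and end dates in SAP 4.1, up to 7 per week.
- Report SABA-free days on the same basis: free days divided by days on study, times 7.
- Limit the rule that sets use to 0 and SABA-free days to 7 to weeks on treatment; later weeks are missing.

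Very short weeks will give unstable values. A minimum number of days for a week to count could be set, or the number of partial weeks shown beside each summary.

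The cost is a few lines of SAP text and about one line of code. No new data are needed, and values for complete weeks are unchanged if the daily scale is kept.

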a determination of a cause unrelated to the IMP or study procedure is made). The specific event or test result (including repeated test results, as applicable) must be recorded both on the source documentation and in the CRF; the adverse events page and/or adverse device effect page and the termination page of the CRF will be completed at that time. The investigator must inform the contract research organization (CRO) as soon as possible of each patient who is being considered for withdrawal due to adverse events. Additional reports must be provided when requested.

If a patient is withdrawn from the study or discontinues IMP for multiple reasons that include adverse events, the relevant page of the CRF should indicate that the withdrawal was related to an adverse event. An exception to this requirement will be the occurrence of an adverse event that in the opinion of the investigator is not severe enough to warrant discontinuation but that requires the use of a prohibited medication, thereby requiring discontinuation of the patient. In such a case, the reason for discontinuation would be “need to take a prohibited medication,” not the adverse event.

In the case of patients lost to follow-up, attempts to contact the patient must be made and documented in the patient’s medical records and transcribed to the CRF.

All assessments should be performed according to the protocol for the end of treatment visit or upon early termination if possible. Patients are required to return the Albuterol eMDPI (used and unused) upon withdrawal from the study.

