3.2. Modified Intent-to-Treat Analysis Set

The modified intent-to-treat (mITT) analysis set is a subset of the ITT analysis set including only patients who receive at least 1 dose of investigational medicinal product (IMP) (IMP is albuterol eMDPI for the DS group and standard-of-care albuterol-administering rescue medication for the CC group) and at least 1 postbaseline assessment on any of the study endpoints (primary, secondary, or exploratory).

In the mITT analysis set, treatment will be assigned based on the treatment to which patients were randomized, regardless of which treatment they actually received. This analysis will be used for all primary, secondary, and exploratory endpoint analyses.

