4. GENERAL ISSUES FOR DATA ANALYSIS

4.1. General

Descriptive statistics for continuous variables include n, mean, standard deviation (SD), standard error (SE), median, minimum, and maximum. Descriptive statistics for categorical variables include patient counts and percentages, missing category will be displayed as appropriate.

Treatment dates are defined as follows:

- Treatment start date: date of randomization/the screening/baseline visit date.
- Treatment end date: the end of treatment/early termination (ET) visit date. If the end of treatment/ET date is missing then the last contact date will be used.

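### Secondary endpoint #2: the zero-use rule is not tied to the patient's treatment end, and the Week 1 reference counts the Day 1 site test inhalation and a part-observed day as a full day

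*SAP*

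**What the plan says.** SAP 6.3.2.1 defines weekly average use as the number of inhalations in the week times 90 ug, divided by 7. SABA-free days are the days in the week without rescue use. All changes are taken from Week 1. For a week with no recorded inhalations: "If no inhalations done for any week, the amount of the SABA use will be 0 and SABA-free days for week will 7".

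SAP 4.4 sets the grid: "Weeks are defined in 7-day intervals (days 1 to 7, 8 to 14, ..., 78 to 84"; and "Day 1 is defined as the treatment start date (i.e., date of randomization/Visit 1 visit date". Day 1 therefore lies inside Week 1. Protocol Appendix B has the eMDPI dispensed during Visit 1, so the device cannot record use earlier that day.

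SAP 8.2 says the first dose is a test at the site on the randomization date. It leaves that dose out of the duration of exposure, and it allows for patients who were not tested that day.

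On withdrawal, Protocol 4.3 says: "Patients are required to return the Albuterol eMDPI (used and unused) upon withdrawal from the study". Such a patient can remain in mITT, which requires one dose and "at least 1 postbaseline assessment on any of the study endpoints (primary, secondary, or exploratory" (SAP 3.2).

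SAP 4.1 does define when treatment ends: "Treatment end date: the end of treatment/early termination (ET) visit date". It adds: "If the end of treatment/ET date is missing then the last contact date will be used". SAP 6.3.2 does not refer to that date. SAP 4.3, on withdrawals and missing data, covers the primary endpoint, SUS, BMQ and BIPQ but not SABA use.

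**The concern.** **Zero-use rule.** With an as-needed drug, a week on treatment without inhalations is a true zero. A week after the inhaler has been handed back is not: no use can be recorded, and the patient is expected to be back on previous rescue treatment. If the rule is programmed as written, those weeks enter the summaries as 0 use and 7 SABA-free days.

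**Partial last week.** If a patient leaves mid-week, the inhalations recorded up to that day are still divided by 7, and the unobserved days count as SABA-free.

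**Week 1 reference.** Every change is measured against a week that contains a supervised test inhalation in tested patients and a day on which use before dispensing is not seen.

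The endpoint has no control group, so nothing in the summaries would reveal an artificial fall in use.

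**Working it through.** The plan gives no figure for this endpoint, so there is none to reproduce; the 0.77 power in SAP 2.4 concerns the primary endpoint. From the documents come the 90 ug, the divisor of 7, the 12 fixed weeks and the 10% dropout. Usage levels, timing of dropout, share of dropouts kept in mITT and time of the Day 1 visit are assumptions, shown as ranges.

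**1. Weeks after withdrawal.** Let D be the dropout rate, spread evenly over 12 weeks, and k the share of dropouts kept in mITT. Assume dropouts use as much as the others. The share of mITT already gone at the start of week i is D·k·((i−1)/12) / (1 − D(1−k)). The group mean falls by that share. The average of (i−1)/12 over Weeks 2-12 is 0.5; at Week 12 it is 11/12.

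- D = 10%, k = 1: 0.10 × 0.5 = 5.0% over Weeks 2-12; 0.10 × 11/12 = 9.2% at Week 12.
- D = 10%, k = 0.5: 0.05 × 0.5/0.95 = 2.6%; 0.05 × 11/12/0.95 = 4.8%.
- D = 15/165 = 9.1% (165 enrolled and 150 evaluable per group), k = 1: 4.5% and 8.3%.
- k = 0: no effect.

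SABA-free days rise by 7·p times the same share, where p is the proportion of days with use. At p = 50% and D = 10%, that is +0.18 and +0.32 day per week for k = 1, and +0.09 and +0.17 for k = 0.5.

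**2. Partial last week.** Take 2 inhalations a day and early termination on Day 38. Week 6 is Days 36-42, with 3 days observed. The formula gives 2 × 3 × 90/7 = 77.1 ug/day; the true rate is 180. The 4 unobserved days count as SABA-free.

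**3. Day 1, tested patient, true use constant.** One test inhalation adds 90/7 = 12.9 mcg/day to Week 1. If a fraction f of Day 1 use precedes dispensing and true use is m inhalations/day, Week 1 also loses (90/7)·f·m. The false later change in mean use is therefore (90/7)(f·m − 1), in mcg/day:

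| Inhalations/day | f = 0.25 | f = 0.5 | f = 0.75 |
|---|---|---|---|
| 0.6 | −10.9 | −9.0 | −7.1 |
| 1 | −9.6 | −6.4 | −3.2 |
| 2 | −6.4 | 0 | +6.4 |
| 4 | 0 | +12.9 | +25.7 |

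The sign turns at m = 1/f. In an untested patient only +(90/7)·f·m remains.

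If the test counts as rescue use, a tested patient with no genuine use on Day 1 loses one SABA-free day from Week 1; one with genuine use loses none. The average false gain in later weeks is 1 − p: +0.7, +0.5 and +0.1 day per week at use on 30%, 50% and 90% of days.

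**4. Check of the remedy.** With constant use, a Days 2-7 mean equals the true rate, and SABA-free days over those 6 days times 7/6 give the true weekly expectation, so both Day 1 errors vanish. Removing only the test inhalation leaves (90/7)·f·m: at f = 0.5 and 1 inhalation/day the error moves from −6.4 to +6.4 mcg/day.

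**The case against.** The best defence is that the SAP can be read sensibly. The endpoint is the "change from week 1 in the number of SABA-free days over the 12-week treatment period", SAP 4.1 gives each patient a treatment end date, and an as-needed drug needs a zero rule. This has force: a reader might infer that post-withdrawal weeks will certainly be mis-scored, and the documents do not support that. But the wording fits the fixed 84-day grid equally well, and 6.3.2.1 does not mention the end date. Protocol 9.3 restricts analysis to observed data only where the SAP does not specify otherwise, and the SAP introduction gives the SAP precedence, so that section does not settle the matter.

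On Day 1, a reader might infer that the SAP is silent, or that 8.2 contradicts 6.3.2.1. Neither holds. SAP 4.4 and the formula set a default: Day 1 counts, over 7 days. SAP 8.2 adjusts only the duration of exposure and still summarizes the number of inhalations without exclusion.

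Nor can it be said that Day 1 is never SABA-free in a tested patient. Whether a supervised test is rescue use is not stated, so that effect is conditional.

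Finally, the endpoint is descriptive, with no decision rule, and most inputs above are assumed. That limits the weight of the point, but not the need for one clear derivation.

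**Conclusion.** The point holds and is minor. As written, the zero-use rule allows unobservable weeks to be scored as the best outcome: about 5% off mean use over Weeks 2-12 and 9% at Week 12, given 10% even dropout, all dropouts kept in mITT and average use among them; nothing if none are kept. A partial last week is understated by the fixed divisor.

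The Week 1 default puts a known test inhalation and a part-observed day into the reference for every change. For a tested patient, if the test counts, this costs Week 1 0 or 1 SABA-free day and adds 12.9 mcg/day, with the partial day working the other way for mean use.

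A reader might infer that correcting this would make the change in mean use less favourable. That does not follow: the number of tested patients is not stated, and the net Day 1 effect can take either sign. The Day 1 and withdrawal effects should not be added together. The primary result, alpha and power are untouched.

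**What to change.** **(a) Zero-use rule.** In SAP 6.3.2.1, apply 0 use and 7 SABA-free days only to complete weeks up to the patient's treatment end date. Set later weeks to missing and report n per week. For a partial last week, either divide by the days observed or set the week to missing, and say which.

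When the ET visit is missing, do not rely on the last contact date alone. Protocol Table 3 (footnote g) has follow-up calls made to patients who ended early, so that date can fall after use stopped. End at the last date the patient is known to hold and use the eMDPI, for example the last eMDPI or App record, or device return.

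**(b) Week 1 reference.** Exclude Day 1: mean use over Days 2-7 divided by 6, and SABA-free days on those days times 7/6. Do not remove the test inhalation alone while keeping the partial Day 1 as a full day.

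**Cost.** SAP wording and derivation code only. Weekly n is slightly smaller (by up to about 15 of 165 DS patients by Week 12 at the planned dropout). The reference rests on 6 days, and it departs from the SAP 4.4 Week 1 that the inhalation flow summaries also use, so the SAP should state the difference.
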